5.7.2 Sample Size Estimation

The proposed sample size is 158 based on sample size calculations for aim 1, as described below.

Power and sample size for aim 1 is based on a standard deviation of radiation exposure of 3 to 3.5 mSv, based on clinical experience, and an anticipated 40% reduction in exposure from 4 to 2.4 mSv. A sample size of 154 (77 per group) will have 80% power to detect a difference in radiation exposure of 1.6 mSv if the standard deviation is 3.5, based on a t test for independent samples with a 5%, two-sided significance level.

Examining power analyses for a noninferiority studies, assuming that the full and reduced methods will produce similar outcomes for image quality and any change in CCTA parameters:

--For the comparison of image quality (aim 1), it is assumed that the image quality for the full method will be 3.2 (standard deviation = 1.1). This study will have power of 80% to show that the mean for the reduced method is at least as high as the mean for the full method. This assumes that the mean image quality scores for the full and reduced populations are 3.20 and 3.15 respectively, with a common within-group standard deviation of 1.10, that a difference of 0.49 points or less is unimportant, that the sample size in the two groups will be 79 and 79, and that

alpha (1 tailed) is set at .05. To accrue complete data 158 subjects, a total of sample size of up to 175 will be recruited to account for a 10% dropout rate for technical difficulties.

--This study will have 81% power to show that the event rate (event rate = any change in CCTA parameters) for the reduced method is at least as low as the event rate for the full method. This assumes that the event rates for the full and reduced method populations are precisely equal (at 50.0%), that a difference of 20% points or less is unimportant, that the sample size in the two groups will be 79 and 79, and that alpha (1 tailed) is set at .05.

While a 20% difference is relatively large, to detect a smaller difference between groups (i.e. difference of 10-15%) using the same assumptions, would require hundreds of subjects.

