During a cardiac CT examination there are typically three phases: acquisition of a scout view for planning the scan length of the examination, obtaining a low dose non-contrast calcium score, and a contrast-enhanced CT coronary angiography for the evaluation of significant coronary artery stenoses. Typically the scan length of the calcium score is based off of the initial scout. The scan length is defined with the use of anatomic landmarks on an anterior-posterior projection image similar to a chest radiograph. For coronary imaging the scan should typically be started at the mid to lower level of the main pulmonary artery, although a location just below the carina is frequently used and should extend through the apex of the heart.

When performed prior to CCTA, calcium scoring can add anywhere from 1-3 mSv to the total radiation dose⁴. Considering that the mean patient effective radiation dose of a CCTA typically ranges from 2-8 mSv, the performance of a typical calcium score that covers the entire heart and proximal aorta adds proportionally considerable radiation to patients undergoing CCTA. This is of particular importance when the imager is implementing strategies for radiation dose reduction and the calcium score may even double the radiation delivered to the patient. During a CCTA the imaging cardiologist or radiologist may modify scan acquisition modes, x-ray tube potential, x-ray tube current, pitch, scan length and scan field of view dependent upon the method of scanning and the system used to reduce the radiation dose of the angiogram. During calcium scoring, image acquisition parameters are typically not dynamically manipulated but are performed in accordance with standard Agatston scoring parameters.¹⁰ Given the additional radiation of the CAC score to the overall radiation dose of the CCTA there has been some uncertainty of whether CAC scoring should be performed in conjunction with CCTA. However, with this approach the imager would lose the potentially useful information regarding the amount and location of the coronary calcium that could impact decision-making in the acquisition parameters in patients that coronary calcium is likely. The imager may also lose the potentially

important information needed to abort a possibly non-diagnostic exam which would ultimately prevent the patient from receiving unnecessary radiation exposure.

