5.7.1 Data Analysis Table

Aim 1- To assess the impact on CCTA image quality using modified calcium score approach.	
 - Image quality (4 point scale) - Signal/noise ratio 	
 - Treatment group - Treatment group 	
 - Two sample t-test or Mann-Whitney (dependent upon the distribution of the data). - Two sample t-test
Aim 2- To determine the rate of changes in the coronary CT angiography acquisition parameters of the modified versus standard calcium scoring	
 - Change in (increase or decrease) in tube current (mA) by 50 - Any change in tube potential (kV) - Change to/from retrospectively-gated CCTA - Any change in padding (acquisition window) - Changing to/from a high definition CT acquisition 	
 - Treatment group 	
 - Fisher's exact test

	All answered as yes/no		
Aim 3- To assess the difference in patient estimated effective radiation exposure (mSv) between the modified versus standard calcium scoring techniques.	- Average of radiation exposure (mSv)	- Treatment group	- Two sample t-test
Aim 4- To assess the difference in patient estimated effective radiation exposure (mSv) of the entire CCTA study (plus calcium scoring) between groups.	- Average of radiation exposure (mSv)	- Treatment group	- Two sample t-test

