5.8. Endpoints

Primary

The measurement of quality in comparison of the modified versus non-modified CCTA using a qualitative (four point scale and measure above) and quantitative (CCTA signal, noise, contrast to noise ratio) score.

Secondary

1. Any changes in the cardiac CT after evaluation of the modified or standard calcium scoring. These changes include: a change in mA by 50, any change in kV, any changes in padding and changing to high definition
2. The measurement of radiation exposure as DLP/milli-sieverts in comparison of the modified versus standard calcium scoring.
3. The measurement of radiation exposure difference measured as DLP/milli-sieverts of the entire CCTA study on the modified versus standard calcium scoring.
4. Whether the imager cancels the study based off of the modified or standard calcium scoring.

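### The radiation power calculation in section 5.7.2 is labelled as Aim 1 (image quality); its inputs do not fit Aim 3, and the 1.6 mSv saving it would need under Aim 4 is not derived

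*Combined protocol and SAP*

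**What the plan says.** Section 5.7.2 opens with "The proposed sample size is 158 based on sample size calculations for aim 1". The next paragraph is about radiation: "Power and sample size for aim 1 is based on a standard deviation of radiation exposure of 3 to 3.5 mSv", with "an anticipated 40% reduction in exposure from 4 to 2.4 mSv". It concludes that 154 subjects (77 per group) give 80% power for a 1.6 mSv difference if the SD is 3.5, using a two-sided 5% t-test. The SD is attributed to clinical experience. The 40% reduction has no stated source.

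The same section then gives a second calculation under the same label: "For the comparison of image quality (aim 1"). This is a one-sided non-inferiority calculation with 79 per group, and the recruitment target follows from it: "To accrue complete data 158 subjects".

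Sections 3 and 5.7.1 define Aim 1 as CCTA image quality, Aim 3 as the radiation dose of the calcium scan, and Aim 4 as the dose "of the entire CCTA study (plus calcium scoring) between groups". Section 5.8 makes image quality primary and both dose comparisons secondary, the Aim 4 endpoint being "The measurement of radiation exposure difference measured as DLP/milli-sieverts of the entire CCTA study on the modified versus standard calcium scoring".

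Section 4.1 (Radiation Exposure) supplies the dose figures: "calcium scoring can add anywhere from 1-3 mSv to the total radiation dose", and a CCTA mean typically between 2 and 8 mSv.

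**The concern.** Two different calculations carry the same aim number: a superiority test in mSv and a non-inferiority test on a four-point scale. Replacing the digit does not settle the matter, because there are two radiation aims and the paragraph does not say whether 4 and 2.4 mSv are calcium-scan doses or whole-study doses.

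Lower dose is the reason for the modified scan, so readers will look for the power of the dose comparisons. As written, neither Aim 3 nor Aim 4 has a power statement under its own name. The 80% could be credited to an aim that it does not describe. A non-significant Aim 4 result could also be read as evidence of no total-dose saving, when the trial may have had little power for the saving that was realistic.

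**Working it through.** **1. Reproducing the plan's radiation figure.** Inputs from 5.7.2: difference 4 − 2.4 = 1.6 mSv (1.6/4 = 40%), SD 3.5, two-sided 5%, two-sample t. The standardised difference is 1.6/3.5 = 0.457. The noncentral t distribution requires 76.09 per group, hence 77 (154 in total), with power 80.5%. At SD 3.0 the same 77 per group give 90.8%. The plan's figure is correct.

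**2. Where 158 comes from.** Image-quality inputs from 5.7.2: margin 0.49, assumed true difference 3.20 − 3.15 = 0.05, SD 1.10, one-sided 5%. The standardised distance is (0.49 − 0.05)/1.10 = 0.40. Power is 79.6% at 77 per group and 80.5% at 79 per group. So 79 + 79 = 158 is the image-quality number; the radiation paragraph gives 154.

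**3. Fit to Aim 3 (calcium scan alone).** Section 4.1 puts this scan at 1-3 mSv. A mean of 4 mSv lies above that range. A variable confined to an interval has an SD of at most half its width, here (3 − 1)/2 = 1.0 mSv. An SD of 3 to 3.5 is not possible within the range.

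**4. Fit to Aim 4 (whole study).** Let c be the CCTA dose, assumed equal in the two arms. The standard scan is then 4 − c, the modified scan is 2.4 − c, and the required cut is 1.6/(4 − c).

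| CCTA dose c (mSv) | Standard scan (mSv) | Modified scan (mSv) | Required cut |
|---|---|---|---|
| 1.0 | 3.0 | 1.4 | 53% |
| 2.0 | 2.0 | 0.4 | 80% |
| 2.4 | 1.6 | 0 | 100% |

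Section 4.1's lower figure for CCTA is 2 mSv, so within that section's figures the cut is 80-100%. The 53% row needs a 1 mSv CCTA, which is below that range. The total of about 2-8 mSv in section 6.2 does not exclude it.

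**5. Sensitivity of Aim 4 power.** Two-sample t, two-sided 5%, 79 per arm. The savings are assumed values; only 1.6 mSv is in the plan.

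| Assumed whole-study saving (mSv) | SD 3.5 | SD 3.0 |
|---|---|---|
| 0.4 | 11% | 13% |
| 0.8 | 30% | 38% |
| 1.2 | 57% | 70% |
| 1.6 | 81% | 91% |

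The saving detectable with 80% power is 1.57 mSv at SD 3.5 and 1.35 mSv at SD 3.0.

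**6. What adjustment could gain.** Covariates explaining a share R² of the dose variance reduce the SD by a factor √(1 − R²). At SD 3.5 the detectable saving falls from 1.57 mSv to 1.57 × √0.8 = 1.40 (R² = 0.2) or 1.57 × √0.5 = 1.11 (R² = 0.5). Both R² values are assumptions.

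**The case against.** The best defence is that this is a labelling slip in a secondary calculation. The sentence already makes its 80% conditional on 1.6 mSv and an SD of 3.5, so it does not claim power for any saving whatever. That stands. The opening sentence, which ties 158 to Aim 1, is also correct once the image-quality calculation is taken as its basis. Nor does a valid trial need a power statement for every secondary endpoint.

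Three stronger readings are tempting, and the documents do not support them.

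- A reader might infer that the sample size is wrong. It is not: 158 reproduces from the image-quality inputs.
- A reader might infer that a 1.6 mSv saving is impossible. The CT Protocol in 5.5 gives the modified scan a lower tube voltage and a shorter length, section 4.1 allows that the calcium scan can double the dose, and CCTA settings may themselves change after the scan. The saving is possible; it is not derived.
- A reader might infer that Aim 4 power really is 11-57%. That range follows if the 40% is applied to a 1-3 mSv scan alone (0.4 to 1.2 mSv), whereas the plan attaches the 40% to the fall from 4 to 2.4 mSv. The lower figures are a sensitivity range only.

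It would also go too far to say that the paragraph must mean Aim 4. If CCTA is at least 2 mSv, a modified-arm total of 2.4 mSv leaves at most 0.4 mSv for the scan, so the fit is strained there too. The authors should say which aim they meant.

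The covariate adjustment proposed below is not needed for validity, since the t-test is valid under randomisation. It is worth having because the covariates are already recorded and the SD is large relative to the expected saving.

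**Conclusion.** The point holds as an internal inconsistency in the power section. The radiation calculation is attached to the wrong aim and cannot describe Aim 3 if section 4.1's 1-3 mSv is taken as the range of scan doses. It is closer to Aim 4, but there it rests on a 1.6 mSv saving with no stated basis. With equal CCTA dose by arm, that saving means an 80-100% cut in scan dose on section 4.1's figures, or 53% if CCTA could be as low as 1 mSv. What is missing is the name of the aim and the basis of the saving.

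The consequence is limited to the secondary radiation aims. Aim 3 measures the scan's own saving directly, so the gap concerns chiefly what the trial can say about total dose. The 1-3 and 2-8 mSv ranges are general figures rather than site data, so the comparison shows a need for explanation and does not prove that the inputs are wrong. The correction should be made, but it is not critical.

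**What to change.** 1. Remove the Aim 1 label from the radiation paragraph, state which radiation aim it serves, and say that 158 rests on the image-quality calculation.
2. Give the source of the 1.6 mSv saving (scan dose, CCTA dose, or both) and show power for smaller savings, marked as assumptions.
3. Do not let the 80% stand for Aim 3. State a mean and SD for that aim on the calcium-scan scale.
4. For Aim 4, keep the planned t-test and add a mean mSv difference with 95% CI, adjusted for BMI, pre-scan heart rate and the CCTA settings proposed before the envelope is viewed (gating, kV, mA, padding, high-definition mode). Section 5.5 fixes these settings before allocation is seen, and the data sheets in 5.5.5 collect all the variables needed (BMI from height and weight).
5. As a minor matter, reconcile section 6.2, which gives about 2-8 mSv for calcium scan plus CCTA, with section 4.1, which gives 2-8 mSv for CCTA alone (and section 6.3, for prospectively triggered scans).

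The cost is some rewording and one extra regression on data already collected. The precision gain is not known in advance, and the radiation power statement becomes narrower. N, the primary analysis and the planned t-test are unchanged.

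### Section 5.7.2 attaches correctly computed non-inferiority power to conclusions worded without the margin, and no later section restores it

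*Combined protocol and SAP*

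**What the plan says.** Section 5.7.2 introduces two calculations with the words "Examining power analyses for a noninferiority studies, assuming that the full and reduced methods will produce similar outcomes for image quality" and acquisition-parameter changes.

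- **Image quality (primary endpoint in 5.8).** The power statement reads "This study will have power of 80% to show that the mean for the reduced method is at least as high as the mean" of the full method. The assumptions follow in the next sentence: "mean image quality scores for the full and reduced populations are 3.20 and 3.15 respectively", a "common within-group standard deviation of 1.10", "a difference of 0.49 points or less is unimportant", "the sample size in the two groups will be 79 and 79", and "alpha (1 tailed) is set at .05".
- **Any change in CCTA parameters (secondary).** The plan claims 81% power to show that the rate with the reduced method is "at least as low as the event rate for the full method". It assumes both rates are 50%, treats a difference of up to 20 percentage points as unimportant, and uses the same group sizes and alpha. It concedes that 20 points is relatively large.

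The table in 5.7.1 lists a two-sample t-test or Mann-Whitney test for image quality and Fisher's exact test for parameter changes, with no margin. Section 5.7.3 refers back to that table. It gives no margin, no confidence interval for these comparisons and no statement of what may be concluded.

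**The concern.** A non-inferiority calculation gives the probability of ruling out a deficit as large as the margin. It does not give the probability of showing that there is no deficit. The two power sentences describe the second claim and attach the probability of the first. For image quality the mismatch is visible within the paragraph, because the planning assumption has the reduced method slightly worse.

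Section 6.2 says that possible loss of CCTA accuracy with the modified scan is what the study investigates. Section 5.7.2 is the only place that says what a positive comparison would show, so its wording sets the claim. A result that excludes only a half-point loss on a four-point scale should not be described as showing no loss.

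**Working it through.** **Inputs (all from 5.7.2).** Means 3.20 (full) and 3.15 (reduced); SD 1.10; margin 0.49; 79 per group; one-sided alpha 0.05. Event rates 50% and 50%; margin 20 percentage points; same n and alpha.

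**1. Reproduce the stated power.**

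Image quality:
- SE = 1.10 × √(2/79) = 0.1750
- Power = Φ((0.49 − 0.05)/0.1750 − 1.645) = Φ(2.514 − 1.645) = Φ(0.869) = 80.8%
- Noncentral t with 156 df gives 80.5%. The n needed for 80% is 78 per group, against 79 stated.

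Event rate:
- SE = √(2 × 0.25/79) = 0.0796
- Power = Φ(0.20/0.0796 − 1.645) = 80.8%, against 81% stated.

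Both figures reproduce, and only with the margins in place.

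**2. What a passing result can look like.** The test passes when the confidence limit lies inside the margin.

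- Image quality: largest passing observed deficit = 0.49 − 1.655 × 0.1750 = 0.200 points (1.655 is the one-sided 5% t value on 156 df). At that result the two-sided 90% interval for reduced minus full is −0.20 ± 0.29, or about −0.49 to +0.09.
- Event rate, with the planning variance: largest passing observed excess = 0.20 − 1.645 × 0.0796 = 0.069, or 6.9 points. The interval is then 6.9 ± 13.1, or about −6.2 to +20.0 points.

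In each case the data favour the full method, the interval includes zero, and the only claim supported is the one with the margin.

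**3. How often this would happen for image quality.** Under the plan's own means and a normal approximation:
- P(pass) = 80.8%
- P(observed reduced mean at or above full mean) = Φ(−0.05/0.1750) = Φ(−0.286) = 38.8%
- P(pass with a lower observed mean) = 80.8% − 38.8% = 42.0%, about half of all passing trials (42.0/80.8 = 52%).

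**4. The sentence without its margin.** A zero-margin test on the same inputs would reject with probability Φ(−0.286 − 1.645) = 2.7% for image quality. For the event rate at exact equality it would reject with probability 5%, which is alpha. These figures confirm that 80% and 81% cannot describe the margin-free claims. They do not measure the design.

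**The case against.** The section labels the analysis as non-inferiority, and each margin appears in the sentence right after the claim. Read together, the intended meaning can be recovered. For the event rate the plan even volunteers that the tolerance is wide. Every power figure is right for its inputs. The aim and the primary endpoint are worded neutrally, and no success criterion or reporting text repeats the margin-free language. All of this stands, and it makes the point minor.

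The passing thresholds above also presuppose a margin-based test, which 5.7.1 does not list. That is correct, and it is why rewording the two sentences is not enough without a decision rule.

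A reader might infer from the 2.7% and 5% that the trial is badly underpowered or that the arithmetic is wrong. The documents do not support that. The figures belong to a zero-margin test that nobody proposed. The first is the chance of reaching a conclusion that is false under the assumed means, and the second is alpha by construction. A reader might also infer that the report will claim parity. Nothing in the documents says so; they only leave the claim unconstrained.

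What the objection does not answer is that the margin is listed as an assumption and never built into the conclusion, and that nothing after 5.7.2 repairs this.

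**Conclusion.** The concern holds as a minor fault of wording. The 80% and 81% are correct for the claims that mean image quality is no more than 0.49 points lower and that the rate of parameter changes is no more than 20 percentage points higher. As written, they are attached to stronger conclusions that the calculation does not support. The size of the gap is an observed deficit of up to about 0.20 points, or an observed excess of up to about 6.9 percentage points, that would still count as a positive result.

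This rests on the plan's own SD, event rate, n and alpha, and on a margin-based comparison being what the power section intends. It does not call the sample size into question.

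**What to change.** In 5.7.2, reword the two power statements:
- *80% power to show that mean image quality with the reduced method is no more than 0.49 points lower than with the full method.*
- *81% power to show that the event rate with the reduced method is no more than 20 percentage points higher than with the full method.*

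In 5.7.1 and 5.7.3, add the matching analysis and decision rule:
- Report each comparison as the difference, reduced minus full, with a one-sided 95% confidence limit (equivalently a two-sided 90% interval), to match the one-tailed alpha of .05.
- Conclude non-inferiority for image quality only if the lower limit is above −0.49, and for the event rate only if the upper limit is below +20 percentage points.
- Do not claim that quality is undiminished, or that changes are no more frequent, unless the limit excludes any deficit or excess.

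The rule is needed because the listed t-test, Mann-Whitney and Fisher tests carry no margin as specified.

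The cost is a few sentences and a less favourable permitted conclusion. The sample size does not change.

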2.1 Purpose

Coronary computed tomography angiography (CCTA) is a frequently performed test for the diagnosis and/or exclusion of coronary artery disease (CAD) in appropriately selected patients¹. The performance of non-contrast computed tomography for the detection and quantification of coronary calcification is typically performed prior to CCTA in an effort to identify significant calcification which may influence subsequent data acquisition during the CCTA. However, performance of calcium scoring adds significant radiation and most coronary calcification is proximal in its location, potentially visualized using a focused non-contrast scan.

The purpose of this study is to prospectively compare the usefulness of a modified non-contrast CT, using a significantly shorter scan length and lower radiation parameters, as compared to standard coronary artery calcium scanning for the detection of coronary calcification that may influence subsequent CCTA performance.

2.2 Research Design:

This is a prospective, randomized single center cohort study to evaluate the diagnostic and clinical impact of a modified versus standard calcium scoring in patients obtaining a coronary CT angiography (CCTA) for the evaluation of symptomatic coronary artery disease.

2.3 Methodology /Technical Approach:

INCLUSION CRITERIA

- 1) Consenting adult patients \geq 50 years of age;
- 2) Suspected but without known prior history of CAD. Prior CAD is defined as a history of myocardial infarction, coronary revascularization or \geq 50% coronary lumen stenosis on prior coronary angiography
- 3) Scheduled for non-emergent clinically indicated coronary CT angiography

EXCLUSION CRITERIA

- 1) Prior coronary bypass graft (CABG) surgery
- 2) Suspicion of acute coronary syndrome (MI or unstable angina)
- 3) Known complex congenital heart disease
- 4) Evidence of ongoing or active clinical instability, including chest pain (sudden onset); cardiogenic shock; unstable blood pressure with systolic blood pressure $<$ 90 mmHg; and severe congestive heart failure (NYHA class III or IV); or acute pulmonary embolism
- 5) Atrial fibrillation
- 6) Abnormal renal function (GFR $<$ 60 ml/min; Creatinine $>$ 1.5 mg/dL)

- 7) Concomitant participation in another clinical trial in which patient is subject to investigation drug or device
- 8) Pregnancy or unknown pregnancy status
- 9) Allergy to iodinated contrast agent
- 10) Contraindications to nitroglycerin
- 11) Unwilling or unable to give consent

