5.7 Statistical Considerations

The statistical evaluation will be performed as seen in the Data Analysis table below in 5.7.1. Of note, all outcomes compare the full and reduced scan groups.

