5.7.3 Data Analysis Plan

1. A patient flow diagram as per CONSORT guidelines will be provided to present the number of subjects recruited, screened, refusals or subjects excluded (with reasons), randomized, lost to follow up, etc. Beginning and ending months of recruitment will be described.
2. A table of baseline demographic and clinical characteristics will be presented for the full and reduced scan groups to include means with standard deviations for continuous normally distributed variables, medians with interquartile ranges for ordinal data and counts with percentages for categorical data. Groups may be compared using two sample t-tests, Wilcoxon rank sum tests or Fisher's exact test as appropriate.
3. Interrater reliability for quality scores will be examined using the Kappa statistic.
4. Univariate comparison of the primary and secondary endpoints are described above in the Data Analysis table.
5. Multivariate analysis of the quality score will include ordinal regression, with the concensus quality score (on a scale from 1 to 4) as the dependent variable and the independent variables to include demographic and clinical factors known to affect CCTA quality, such as BMI, breath-holding, resting heart rate, use of nitroglycerin, etc.

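### Aim 2 is powered as a 20-point non-inferiority test on any CCTA parameter change, but the governing analysis table names only Fisher's exact test, with no margin or interval

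*Combined protocol and SAP*

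**What the plan says.** **Powered hypothesis.** Section 5.7.2 places Aim 2 under its non-inferiority power analyses. The outcome is a composite ("event rate = any change in CCTA parameters"). The aim is to show that the rate "for the reduced method is at least as low as the event rate for the full method", on the footing "that a difference of 20% points or less is unimportant". The assumptions are 50% in both arms, 79 per arm and a one-tailed alpha of 0.05; the stated power is 81%.

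**Planned analysis.** Section 5.7 states: "The statistical evaluation will be performed as seen in the Data Analysis table below in 5.7.1". Section 5.7.3, item 4, repeats this: "Univariate comparison of the primary and secondary endpoints are described above in the Data Analysis table". In that table the Aim 2 row lists five items (tube current, tube potential, retrospective gating, padding, high definition), marks them "All answered as yes/no", and gives the test as "Fisher's exact test". It has no margin, interval or sidedness, and no row for the composite. Nothing else in 5.7.3 adds a non-inferiority analysis.

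**Event definition.** Section 3 and the 5.7.1 table count changes to or from retrospective gating and to or from high definition. The lists in 5.5 (Methods) and 5.8 (first secondary endpoint) leave out gating and mention only a change to high definition.

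**The concern.** The hypothesis that was powered and the test that was planned answer different questions. Fisher's test asks whether the two rates differ. The non-inferiority test asks whether an excess of 20 points or more can be excluded. Failing to find a difference does not exclude an excess of that size, least of all with 79 patients per arm.

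A team that follows 5.7.1 to the letter will have a p-value and no planned means of reaching the conclusion for which 5.7.2 claims 81% power. The risk is that p > 0.05 is then reported as though it were that conclusion. In addition, because the component lists differ, one patient could count as an event under section 3 and not under 5.8, so the powered rate is not uniquely defined.

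**Working it through.** **Inputs.** From 5.7.2: 79 per arm, 50% in both arms, margin 0.20, one-tailed alpha 0.05 (z = 1.645). From 5.7.1: Fisher's exact test. Assumptions made here: Fisher is two-sided at 5% and applied to the composite, because the table states neither. True modified rates of 60% and 70% are scenarios chosen for illustration; 70% is the plan's 50% plus its own margin.

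**Step 1: reproduce the plan's 81%.**
- Standard error at 50% vs 50%: √(2 × 0.5 × 0.5 / 79) = √(0.5/79) = 0.0796.
- Power = Φ(0.20/0.0796 − 1.645) = Φ(2.514 − 1.645) = Φ(0.869) = 80.8%.
- Enumerating all binomial outcomes for the same (Wald) margin test gives 80.9%.

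The stated figure is right, but for a margin-based test.

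**Step 2: compare the two rules.** The same enumeration was run with the standard rate at 50%. The margin test is met when the upper limit of the two-sided 90% Wald interval for modified minus standard is below +20 points.

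| True modified rate | Margin test met | Fisher non-significant | Fisher non-significant and margin test failed |
|---|---|---|---|
| 50% | 80.9% | 96.9% | 17.5% |
| 60% | 34.9% | 81.2% | 46.3% |
| 70% | 4.6% | 32.4% | 27.7% |

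The 70% row carries the point. There the true excess equals the margin, so non-inferiority should be concluded in no more than about 5% of trials. The margin test respects that (4.6%). Reading non-significance as non-inferiority would give that conclusion in 32% of trials.

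The 17.5% and 46% in the other rows are of another kind. In those rows the modified scan is truly within the plan's margin, so they count inconclusive trials, not false conclusions.

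**Step 3: one concrete result.** Suppose 48/79 modified and 40/79 standard patients have a change.
- Difference: 0.608 − 0.506 = 0.101, or +10.1 points.
- Standard error: √[(0.608 × 0.392 + 0.506 × 0.494)/79] = 0.0786.
- One-sided 95% upper limit: 0.101 + 1.645 × 0.0786 = 0.231, or +23.1 points (+22.6 by Newcombe's method).
- Fisher's p = 0.26.

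There is no significant difference, yet a 20-point excess is not excluded, so the hypothesis in 5.7.2 is not shown.

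**The case against.** **The composite can be recovered.** Section 3 defines a significant change as any one of the listed items, and 5.8 also speaks of any changes. This stands: the missing composite row is a gap in the table, not a conflict over the outcome. It does not supply the margin or the interval.

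**The margin in 5.7.2 implies the analysis.** A sensible analyst might infer it. But two places direct the analysis to 5.7.1, which names a different test, and no section says how the margin is to be applied.

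**The harm is conditional, and the aim is secondary.** Both are true. Nowhere does the plan say that p > 0.05 will be read as non-inferiority, and the sample size of 158 is attributed to Aim 1. This limits the weight of the point. Still, the plan gives Aim 2 its own power statement, so it should also give the analysis to which that power belongs.

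**A stronger reading.** Section 2.1 says the pre-scan is there "for the detection of coronary calcification that may influence subsequent CCTA performance". A reader might infer that the plan is mis-aimed, because a shorter scan that misses calcium could prompt too few changes and still pass. A true 30% vs 50% would indeed meet the margin test more than 99.9% of the time. The documents do not support calling this a defect. A one-directional hypothesis is a legitimate choice for a secondary endpoint, a lower rate is consistent with it, and the plan nowhere claims that no changes were missed. Image quality (primary) and cancellation of the study (secondary) are assessed separately. What remains is a limit on interpretation.

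**The shorter event lists need not be exhaustive.** Both are introduced as what the changes include, and the data sheet in 5.5.5 records gating before and after the calcium scan. No data would be lost, so this is a minor point of consistency.

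**Conclusion.** The concern holds as a mismatch between the powered hypothesis and the planned analysis. The 81% is arithmetically sound, but it belongs to a margin test that 5.7.1 and 5.7.3 do not contain, and Fisher's test cannot deliver the conclusion. At a true excess equal to the margin, the gap is 32% of trials non-significant on Fisher against 4.6% meeting the margin test. This assumes 79 evaluable per arm, a 50% standard rate, and a two-sided 5% Fisher test on the composite.

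Two larger claims should not be drawn. The 17.5% and 46% are not error rates. Nor is the plan shown to be wrong in testing only one direction. The difference in event lists is a minor matter to reconcile. Overall this should be fixed, at the weight of a secondary aim.

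**What to change.** 1. In the Aim 2 row of 5.7.1, name any CCTA parameter change (yes/no) as the outcome. Analyse it by the modified-minus-standard difference in rates with a two-sided 90% confidence interval, naming the method (Newcombe's, for example). Conclude non-inferiority only if the upper limit is below +20 points. Keep Fisher's test as descriptive for the five separate items.
2. Report both limits of the interval, with no added criterion at −20 points, since the plan sets none. State that meeting the upper limit will not be interpreted as showing that no changes were missed.
3. Bring the event lists in 5.5 and 5.8 into line with section 3 and 5.7.1 (gating; to or from high definition), so that any change is one defined event.

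**Cost.** Wording in three sections and one confidence interval, from data the plan already collects. Sample size and the 81% power are unchanged. The downside for the sponsor is that a non-significant Fisher result can no longer be presented as showing non-inferiority.
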